### 3. Summary of the project

Since 2017, a Multispectral Optoacoustic Tomograph (MSOT) with an extended emission spectrum is available to the University Hospital Erlangen through a DFG large-scale equipment funding. For MSOT imaging, similar to conventional sonography a transducer is placed on the skin, and instead of sound, energy is applied to the tissue by means of pulsed laser light. This leads to a constant change of minimal expansion and contraction of individual tissue components or molecules. The resulting sound waves can then be detected by the same device. Previous studies have already shown that the quantitative determination of haemoglobin can provide information on blood flow and inflammatory activity in chronic inflammatory bowel diseases. In the extended spectrum other markers such as collagens and lipids can be detected in addition to haemoglobin and its oxygenation status. We were able to show with our experimental preliminary work and a large animal pig model that an *in vivo* quantification of collagen is possible. In the first application of MSOT in children with Duchenne muscular dystrophy, the measured collagen content correlated with the clinical function tests. In summary, we could show that the molecular muscle structure quantified by MSOT allows the establishment of new, age-independent, non-invasive molecular biomarkers for disease assessment and therapy monitoring in patients with DMD.

Neuromuscular diseases often present as early as in neonatal age and manifest themselves in muscular hypotonia and weakness. Associated diseases are caused by numerous pathologies in the central nervous system (brain and spinal cord), the peripheral nervous system or skeletal muscle. X-linked progressive muscular dystrophy of the Duchenne type (DMD) is one of the most common progressive muscular diseases of childhood with an incidence of 1:3500 male newborns and is primarily associated with a reduced life expectancy. Around the age of 4-5 years, motor problems manifest themselves in everyday life with typical signs of proximal muscle weakness and laboratory chemical increase of the muscle enzyme (creatinine kinase, CK). Within a few years, relevant muscle and tendon shortenings develop, leading to joint malpositions, instabilities, and consecutively to scoliosis and loss of walking around the age of 10. Supportive therapy measures cannot curatively influence complications and progression of the disease. Pathogenetically, there is a deficiency of dystrophin, a structural protein of the sarcolemma, which is caused by mutations (mostly deletions) of the dystrophin gene (Xp21.3-p21.2). The consequence of dystrophin deficiency is necrosis of the muscle cells which are replaced by connective tissue and fat. The 6-minute walk test (6-MWT) is usually used to quantitatively assess the disease progression as well as the effects of therapy. In this test, the patient need to walk as much distance as possible within 6 minutes. However, this test is dependent on cooperation and is usually not successful in the very young patients. The effects of new gene therapeutic therapies (e.g. PTC 124) are currently still being

assessed with the help of this clinical function test. Sensitive, non-invasive methods for measuring muscle degeneration at an early stage and muscle function during the course of the disease are therefore of great clinical and scientific importance.

The MSOT data collected so far seem promising to enable therapy monitoring in DMD patients. Preliminary work by other groups has already demonstrated a very good precision and reproducibility of MSOT. However, it has not yet been investigated to what extent 1) previous physical activity, 2) different measurement positions of the muscle, 3) different examination dates and 4) intra- and interrater variability influence the measurement results. Especially molecular changes immediately after the 6-MWT are relevant for studies in muscle patients with DMD.

In this first pilot study, the aim is to investigate in healthy adults whether increased exercise alters haemoglobin values, the collagen content remains constant and repeated measurements at different muscle positions by different investigators provide consistent measurement results over time. This information is essential for further studies of children with neuromuscular disorders to properly evaluate a possible response to therapy.

### Sponsoring

Children's Hospital Erlangen, Else-Kröner-Fresenius Foundation (Else-Kröner-Fresenius

Memorial Scholarship [name])

## 5. Scientific background

Since 2017, the University Hospital Erlangen (Medical Clinic 1, Pediatric and Adolescent Clinic) has a Multispectral Optoacoustic Tomograph (MSOT) funded by the DFG. This allows non-invasive, quantitative imaging of the composition of target tissues in the non-sedated child, comparable to sonography. This is of particular importance in this patient group.

In MSOT, similar to conventional sonography, a transducer is placed on the skin and instead of sound, energy is supplied to the tissue by means of pulsed laser light. This leads to a constant change of minimal expansions and contractions (thermoelastic expansion) of individual tissue components or molecules. The resulting sound waves can then be detected by the same examination unit. Previous studies have shown that the quantitative determination of hemoglobin can be used to obtain information on blood flow and inflammatory activity in the intestine from patients with Crohn's disease (Waldner, Knieling et al. 2016, Knieling, Neufert et al. 2017) (Waldner 2016, Knieling 2017). In the newly configured device (Acuity Echo, iThera Medical GmbH, Munich, prototype) an extended spectrum of laser light can be used, which ultimately not only enables the detection of haemoglobin and its oxygenation stages, but also the detection of further markers such as collagen and lipid. This principle has already been successfully used in a follow-up study on pediatric patients with Duchenne muscular dystrophy (Regensburger, Fonteyne et al., submitted for publication, ESMI Young Investigator Award 2019).

[figure not shown]
[figure not shown]

Figure 1 - MSOT principle (a), experimental preliminary work (b), and first time representation of collagen *in vivo* (c)

We were able to show by our experimental preliminary work and a large animal pig model that an in vivo quantification of collagen is possible. In the first application of MSOT in children with Duchenne muscular dystrophy, the measured collagen content correlated with the clinical function tests. In summary, we could show that the molecular muscle structure quantified by MSOT allows the establishment of new, age-independent, non-invasive molecular biomarkers for disease assessment and therapy monitoring in patients with DMD.

Neuromuscular diseases often present as early as in neonatal age and manifest themselves in muscular hypotonia and weakness. Associated diseases are caused by numerous pathologies in the central nervous system (brain and spinal cord), the peripheral nervous system or skeletal muscle. X-linked progressive muscular dystrophy of Duchenne type (DMD) is one of the most common progressive muscular diseases of childhood with an incidence of 1:3500 male newborns and is primarily associated with a reduced life expectancy (Mendell and Lloyd-Puryear 2013). From the age of 4-5 years, motor problems

manifest in everyday life with typical signs of proximal muscle weakness and laboratory chemical increase of the muscle enzyme (creatinine kinase, CK). Within a few years, relevant muscle and tendon shortenings develop, leading to joint malpositions, instabilities, and scoliosis and loss of walking around the age of 10. Supportive therapy measures cannot curatively influence complications and progress of the disease. Pathogenetically, there is a deficiency of dystrophin, a structural protein of the sarcolemma, which is caused by mutations (mostly deletions) of the dystrophin gene (Xp21.3-p21.2). The consequence of dystrophin deficiency is necrosis of the muscle cells which are replaced by connective tissue and fat (Hoffman, Brown et al. 1987, Klingler, Jurkat-Rott et al. 2012, Mercuri and Muntoni 2013). The 6-minute walk test (6-MWT) (McDonald, Henricson et al. 2010, McDonald, Henricson et al. 2010, Bushby, Finkel et al. 2014, Mendell, Goemans et al. 2016, McDonald, Campbell et al. 2017) is usually used for the quantitative assessment of the disease progression as well as therapy effects. Here the patient needs to walk the longest distance possible within 6 minutes.

However, this test is dependent on cooperation and is usually not successful in very young patients. In addition, daily fluctuations in the patients' function and strength as well as learning effects can influence the results. A problematic and limiting factor for the use of the 6MWT as a reliable marker is that progressive muscle degeneration is only detected functionally at a late stage. MRI studies to characterize the degenerative changes in early-stage skeletal muscles show promising results in order to find quantitative measures to determine edematous changes and fatty degeneration (Arpan, Willcocks et al. 2014, Bonati, Hafner et al. 2015, Glemser, Jaeger et al. 2017, Barnard, Willcocks et al. 2018). For clinical use, the required sedation of the patients may be limiting for the feasibility of MRI diagnostics. The highly sensitive assessment of therapeutic effects is expected to become increasingly important in the future. In the meantime, the detection of a nonsense point mutation leading to a premature stop codon and thus to the premature termination of protein synthesis has therapeutic consequences. For walkable boys with DMD with a proven nonsense mutation, a gene therapy approach with PTC 124 (Translarna®, Ataluren, PTC Therapeutics) has been available since 2016 which leads via ribosomal read-through to the formation of functionally active full-length dystrophin and to a significant improvement of muscle function (Bushby, Finkel et al. 2014, McDonald, Campbell et al. 2017). Methods for assessing the efficacy are controversially discussed and are not standardized established in clinical practice. Sensitive, non-invasive methods for recording muscle degeneration at an early stage and muscle function during its course are therefore of great clinical and scientific importance.

The MSOT data collected so far seem promising to enable therapy monitoring in DMD patients. Preliminary work by other groups has already demonstrated a very good precision (Joseph, Tomaszewski et al. 2017) and reproducibility (Helfen, Masthoff et al. 2019) of MSOT measurements (with a technically slightly different prototype). However, no investigations have been carried out so far:

- to what extent physical activity influences the measurement results
- the extent to which the MSOT values vary within a muscle (different muscle positions)
- whether the measured values change over time, and
- whether the intra- and interrater differences also apply to this MSOT prototype

In this first pilot study, the aim is to investigate in healthy adults whether increased exercise changes the haemoglobin values, the collagen content remains constant and repeated measurements at different positions and by different examiners over time provide consistent measurement results. This information is essential for planning further studies in children with neuromuscular disorders, and to be able to evaluate a possible response to therapy.

## 6. Study objectives

The aim of the proposed study is a longitudinal comparison of muscle tissue composition based on Multispectral Optoacoustic Tomography (MSOT) of healthy, adult subjects, before and after physical exercise.

### Primary/secondary objectives and/or hypotheses

#### *Hypotheses:*

- The quantitative amount of hemo/myoglobin signal in muscles of healthy volunteers determined by MSOT differs *before and after the 6-minute walk test*.
- The quantitative amount of oxygenated/deoxygenated hemo/myoglobin signal in muscles of healthy volunteers determined by the MSOT differs *before and after the 6-minute walk test*.
- The quantitative amount of collagen signal in muscles of healthy volunteers determined by MSOT does not differ *before and after the 6-minute walk test*.
- The quantitative amount of hemo/myoglobin signal in muscles of healthy volunteers determined by the MSOT does not differ when *the follow-up is measured after 2 weeks*.
- The quantitative proportion of oxygenated/deoxygenated hemo/myoglobin signal in muscles of healthy volunteers determined by MSOT does not differ when *the follow-up is measured after 2 weeks*.
- The quantitative proportion of collagen signal in muscles of healthy volunteers determined by MSOT does not differ when *the follow-up is measured after 2 weeks*.
- The quantitative proportion of hemo/myoglobin signal in muscles of healthy volunteers determined by MSOT does not differ *within a muscle* of healthy volunteers.
- The quantitative proportion of oxygenated/deoxygenated hemo/myoglobin signal determined by MSOT does not differ *within one muscle* of healthy volunteers.
- The quantitative fraction of collagen signal determined by MSOT does not differ *within one muscle* of healthy subjects.
- The quantitative amount of hemo/myoglobin determined by MSOT does not differ *between two measurements by the same examiner*.
- The quantitative amount of oxygenated/deoxygenated hemo/myoglobin determined by the MSOT does not differ *between two measurements by the same examiner*.
- The quantitative amount of collagen determined by the MSOT does not differ *between two measurements by the same examiner*.
- The quantitative amount of hemo-/myoglobin determined by the MSOT does not differ *between measurements made by two different examiners*.

- The quantitative amount of oxygenated/deoxygenated hemo-/myoglobin determined by the MSOT does not differ *between measurements performed by two different examiners*.
- The quantitative amount of collagen determined by the MSOT does not differ *between measurements made by two different examiners*.

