## 7. Target parameters

All measurements with MSOT are performed at three muscle positions of the proximal and distal lower extremity muscles in lateral comparison (right - left, leg proximal: Musculus quadriceps, distal: Musculus gastrocnemius) by two different examiners, in healthy subjects, at two different timepoints.

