#### ***Statistical methods:***

The data are given as mean value with standard deviation. Correlations are specified with the parametric Pearson correlation coefficient (R). According to the distribution between timepoint 1 and timepoint 2, the differences of the mean values are statically examined with a parametric T-test. In all analyses, an error level of <0.05 is considered statically significant.

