Non-invasive molecular imaging to determine the hemoglobin and collagen content in muscles before and after physical exercise and over time (MSOT_muscles)

Unique Protocol ID: 169_19B

ClinicalTrials.gov Identifier: NCT03979157

Version date: 23.04.2019

Sponsor:

Department of Pediatrics and Adolescent Medicine
University Hospital Erlangen
Friedrich-Alexander-University (FAU) Erlangen-Nürnberg
Pediatric Experimental and Translational Imaging Laboratory (PETI-Lab)
[name]
[name]
[contact]

Statistical Analysis Plan

The present study is a pilot proof-of-concept study. Due to lack of clinical trials in this area, the comparative changes of MSOT spectra and signals within and between examiners, before and after exercise, over time and between different muscles and muscle positions are unknown. Therefore, no sample size calculation was performed.

The primary outcome measure is to assess the reproducibility of the muscular optoacoustic spectra of healthy volunteers facing different variables (examiner, time, exercise, muscle position).

MSOT signals are derived from averaged video captures (seven frames) obtained in anatomical independent muscle regions in patients. All anatomical locations are considered independent. In cases of multiple scans/recordings, a mean of all analyzed scans is calculated.

Continuous variables are given as means and standard deviations; categorical variables are provided as numbers and percentages. Data are tested for normal distribution using Shapiro-Wilk test prior to inferential analysis. MSOT signals are compared matched manner using a paired t-test when parametric and a Wilcoxon matched-pair signed rank test when non-parametric. For the comparison of three or more groups analysis of variance (ANOVA) and for nonparametric distribution Friedman Test is used. Correlations are specified with the parametric Pearson correlation coefficient (r) and the nonparametric Spearman correlation (r_s), using a 95% confidence interval. Additionally, the intraclass correlation coefficient (ICC) will be used with the grading proposed by Landis and Koch. For all analysis an error level of $p < 0.05$ is considered as statistically significant. All analyses are performed using GraphPad Prism (Version 8, GraphPad Software, La Jolla, CA, USA) and/or IBM SPSS Statistics (Version 24, IBM Corp., N.Y., USA).

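### Thirteen of 15 hypotheses predict no difference but are examined with difference tests that cannot support them; separately, counting locations as independent distorts the p-values for all 15

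*Protocol*

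**What the plan says.** Protocol section 6 (Hypotheses) lists 15 statements. Two predict a change after the walk test: total hemo/myoglobin, and its oxygenated/deoxygenated components. The other 13 predict no change. One concerns collagen around the walk test: "The quantitative amount of collagen signal in muscles of healthy volunteers determined by MSOT does not differ". The remaining 12 take the three signals (total hemo/myoglobin, oxygenated/deoxygenated, collagen) over two weeks, within a muscle, between two measurements by one examiner, and between two examiners.

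For timepoint 1 against timepoint 2, Protocol section 12 (Statistical methods) says "the differences of the mean values are statically examined with a parametric T-test". The SAP says "MSOT signals are compared matched manner using a paired t-test when parametric", with a Wilcoxon test otherwise, and "For the comparison of three or more groups analysis of variance (ANOVA) and for nonparametric distribution Friedman Test is used". Both documents use p<0.05. The SAP makes reproducibility the primary outcome and adds: "Additionally, the intraclass correlation coefficient (ICC) will be used with the grading proposed by Landis and Koch".

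On the unit of analysis the SAP says "All anatomical locations are considered independent" and "In cases of multiple scans/recordings, a mean of all analyzed scans is calculated". Protocol section 7 says "All measurements with MSOT are performed at three muscle positions of the proximal and distal lower extremity muscles in lateral comparison". Section 10 (Measurements) confirms two muscles on both sides, with two scans per examiner at each position. Section 9 plans 10 volunteers.

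**The concern.** There are two defects, and they need different repairs.

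The first is the form of inference. A t-test, Wilcoxon, ANOVA or Friedman test takes no difference as its null hypothesis. It can reject the 13 hypotheses but cannot confirm them. Neither document plans a confidence interval for a mean difference, limits of agreement, a within-subject SD or an equivalence margin, and no rule says what p>0.05 means. Protocol sections 3 and 5 present the results as essential for later studies in children and for judging response to therapy. Those studies need to know how large a drift, position effect or examiner shift remains compatible with the data, which a p-value does not tell them.

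The second is the unit. If the 12 locations of one person are treated as 12 independent observations, standard errors are too small whenever the paired differences correlate within that person. This reaches the two change hypotheses as well, where a false positive would favour the predicted result.

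**Working it through.** **Inputs.** 10 volunteers (Protocol section 9). Locations per volunteer: 3 positions x 2 muscles x 2 sides = 12 (sections 7 and 10). Pairs: 10 x 12 = 120, or 10 x 4 = 40 if the three positions are averaged to one value per muscle-side. Alpha is 0.05; two-sided is assumed. The documents give no SD, correlation, margin or power figure, so there is nothing to reproduce, and effect sizes and correlations below are assumptions shown as ranges.

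**Count.** Two hypotheses predict a difference; 1 + 3 + 3 + 3 + 3 = 13 predict none.

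**1. What non-significance is worth at the volunteer level.** For a true shift of d SDs of the volunteer-level differences, the chance of p>0.05 is P(|T| < 2.262), where T is noncentral t with 9 df and noncentrality d x sqrt(10). For d = 0.3, 0.5, 0.8 this is 0.864, 0.707, 0.384.

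**2. The unit, paired t-test.** Differences are simulated as normal with equal correlation within a volunteer. With m locations the variance of the overall mean is inflated by 1 + (m-1) x correlation; for m = 12 and correlation 0.3 that is 4.3, so 120 pairs carry the information of 120/4.3 = 28.

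| Correlation of differences | 0 | 0.1 | 0.3 | 0.5 |
|---|---|---|---|---|
| No shift, significant: 120 pairs | 5% | 17% | 35% | 45% |
| No shift, significant: 40 pairs | 5% | 9% | 16% | 22% |
| No shift, significant: one mean per volunteer | 5% | 5% | 5% | 5% |
| Shift 0.3 location-level SD, missed by volunteer means | 17% | 47% | 71% | 79% |
| Same shift, missed by 120-pair test | 10% | 18% | 25% | 28% |

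In the 40-pair row the correlation is that between muscle-side differences. The fourth row follows from step 1: the SD of a mean of 12 is sqrt((1 + 11 x correlation)/12) = 0.289, 0.418, 0.599, 0.736, so 0.3 SD becomes d = 1.04, 0.72, 0.50, 0.41. Steps 1 and 2 use different SD scales and should not be compared directly. The 120-pair test misses less in the last row partly because it also rejects too often when nothing has changed.

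**3. Three positions, matched ANOVA.** The matched form is an assumption; the SAP says only ANOVA. A volunteer effect common to all positions cancels, and the false-positive rate stays about 5%. It rises only if a volunteer-by-position effect is shared across blocks. At correlations 0.1, 0.3, 0.5 it is then 10%, 21%, 31% with 40 muscle-sides, or 7%, 10%, 14% for one muscle with 20 blocks. An unmatched one-way ANOVA on 10 volunteers errs the other way: 2.6% and 0.6% at between-position correlations of 0.2 and 0.5. For a 0.5 shift of one position (in SDs of the block-level paired differences), a volunteer-level analysis misses about 14%, 24%, 42%, 54% at correlations 0, 0.1, 0.3, 0.5; taking 40 blocks as independent misses 9%, 11%, 14%, 15%.

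**4. The ICC.** Set the between-volunteer variance to 1. A consistency ICC of 0.90 implies error variance 1/0.90 - 1 = 0.111. A constant examiner shift of 0.5 between-volunteer SD adds examiner variance 0.5^2/2 = 0.125. The consistency ICC stays 0.90; absolute agreement is 1/(1 + 0.111 + 0.125) = 0.81. An observed ICC of 0.80 from two readings has a 95% interval (exact F) of 0.38 to 0.95 with 10 volunteers, but 0.72 to 0.86 if 120 locations count as independent.

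**The case against.** The study is declared exploratory (Protocol section 6, Study type) and has no sample size calculation. The SAP does supply an agreement statistic with a grading scale for its reproducibility outcome, and the 95% interval it mentions for correlations may be meant to cover the ICC too. This stands as a limit on severity, and it argues for estimation rather than formal equivalence testing. It does not close the gap: the ICC is not tied to any hypothesis, and a consistency form would miss a constant shift.

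A reader might infer that the sponsor will present p>0.05 as proof of agreement. The documents do not say so; they are silent on how such a result will be read, and that silence is the defect.

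A reader might also take 45% as the plan's false-positive rate. No correlation is given, and at zero there is no inflation. The SAP's wording about muscle regions can fairly be read as four units per volunteer, hence the 40-pair row. If independence means that each location is tested separately, n is 10 and step 1 applies instead. Nor is the position ANOVA necessarily too liberal: step 3 shows inflation, none, or the reverse, depending on the model.

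**Conclusion.** The point holds and should be fixed before analysis. That difference tests cannot support 13 of the 15 hypotheses needs no assumption about the data. How often a real shift would go unnoticed does: 86%, 71% and 38% for 0.3, 0.5 and 0.8 SD of the volunteer-level differences, assuming normality and a two-sided 5% test. The unit problem is a separate defect affecting all 15 hypotheses. Its size depends on an unknown correlation, from no inflation at zero to 45% (120 pairs) or 22% (40 pairs) at 0.5. The collected data remain fully usable; what needs repair is the inference drawn from them. The documents do not support a claim that the study is invalid, that it needs more volunteers, or that it must run equivalence tests.

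**What to change.** 1. Delete the SAP sentence "All anatomical locations are considered independent" and treat the volunteer as the cluster for all 15 hypotheses. Either use one value per volunteer (for position contrasts, one per volunteer per position, separately for each muscle), or fit a mixed model with volunteer random effects and small-sample degrees of freedom. The model needs fixed terms for muscle and position, interacting with the comparison where muscle-specific effects matter; a volunteer random effect alone would not reveal an effect confined to one muscle.
2. For the 13 no-difference hypotheses, report the mean difference or contrasts with 95% confidence intervals, limit conclusions to the differences the interval excludes, and state that p>0.05 is not evidence of agreement.
3. Specify the absolute-agreement ICC, with a 95% interval that respects the cluster, and name the hypotheses it serves. Use individual scans, not their mean, for the same-examiner comparison. Limits of agreement or the within-subject SD would be a useful addition.
4. Keep difference tests for the two change hypotheses, at the same unit. Equivalence testing is optional, with a margin fixed in advance.

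The cost is SAP wording and modest extra analysis, with no new data. The downside is wider intervals: at n = 10 the 95% half-width is 2.262/sqrt(10) = 0.72 SD of the volunteer-level differences, so many no-difference claims will be inconclusive. Optional equivalence tests (two one-sided 5% tests, true difference zero) would have power of about 7%, 52% and 79% for margins of 0.5, 0.8 and 1.0 SD.
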